#### **Statistical Issues**

Analytic Approach. Summary statistics (means, SDs, ranges, frequencies) will be computed for all variables of interest and compared between the treatment arms at baseline using 2-sample tests to test if randomization achieved balance in key covariates across groups. In the event of pre-existing variable group differences associated with dependent or relevant clinical variables, the nuisance variables will be statistically controlled. Outcome measures (e.g. health-related behaviors, psychological health, and objective measures of microbiome health and inflammation) will be transformed as needed to better approximate Gaussian distributions. The proposed study period is 2 months; hence we anticipate little loss-to-follow-up. However, subjects may drop out for a variety of reasons. It is important to take missing data into account when testing hypotheses of interest. Mixed-models can be applied even if some observations are missing as long as the data are "missing at random". Missing data (e.g., drop-outs) will be tested to determine if it is informative, and the methods to test for completely random dropouts will be applied. If needed, pattern-mixture models will be developed which take "missingness" into account when estimating parameters of interest using the methods of Park & Lee.

Analysis Plan. Two sample *t*-tests will be used to compare change scores (post-treatment minus pretreatment) in each outcome. Given the multiple outcomes, we will also use O'Brien's test which can be used to compare multiple endpoints across groups; we will apply O'Brien's test to the multiple outcomes for each hypothesis (e.g., psychological health via positive and negative affect, depressive symptoms; health behaviors via diet, physical activity, medication adherence, and alcohol usage). The O'Brien test statistic is a weighted linear combination of the *t*-statistics for each outcome. Finally, we will fit mixed effects models, with a subject-specific intercept included to allow for individual variability in outcome. Main covariate effects will be treatment group, time (pre-treatment and immediately post-treatment), and the group X time interaction. Likelihood ratio tests will be used to test the significance of these covariates. A significant group X time interaction will indicate that outcome trajectories differ across treatment groups.

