Sample Size and Power. We hypothesized a Cohen's *d* effect-size (standardized mean difference between groups) of 0.75 based on previous studies. With at least 60 subjects completing 2 visits, we will have 80% power (2-sided alpha=0.05) to detect a 0.75 effect-size (Cohen's *d*). To be conservative, we aim to recruit 75 subjects to this study, allowing for a 20% drop-out/loss-to-follow-up rate and a total of 60 subjects completing the 2 visits. Note that our calculations did not control the Type I error for the multiple endpoints. Our objective in this small pilot study is to obtain early evidence of the putative efficacy of this novel intervention on a multitude of outcomes, psychosocial and biological, in the elderly. We expect our findings to inform the design of a larger future clinical trial in elderly subjects.

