#### **10. HUMAN SUBJECTS**

This project will recruit 75 and test a total of 60 healthy elderly subjects from UCSD ADRC. We aim to test 60 participants (20 per group, 3 groups) from UCSD.

Patients who are elderly and cognitively intact will be identified, screened, and recruited from UCSD ADRC following the procedures outlined in Section 11 below.

Study testing visits will take place at SOM Building 4.

Along with the referring physician, [name] will oversee determination of whether potential subjects fit eligibility criteria according to the criteria outlined below.

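### The mixed-model likelihood ratio tests have no small-sample correction; with the default chi-square reference, the three-arm group-by-time test has a true size of about 5.8% at nominal 5%

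*Combined protocol and SAP*

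**What the plan says.** The Analysis Plan paragraph in section 9, Statistical Issues, lists three analyses.

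- Two-sample t-tests, which "will be used to compare change scores (post-treatment minus pretreatment) in each outcome".
- O'Brien's test, applied to the set of outcomes under each hypothesis.
- Mixed models "with a subject-specific intercept included to allow for individual variability in outcome". Their terms are described as follows: "Main covariate effects will be treatment group, time (pre-treatment and immediately post-treatment), and the group X time interaction". Then: "Likelihood ratio tests will be used to test the significance of these covariates". A significant interaction is to be read as evidence that the arms follow different courses.

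The expected sample is small. The Sample Size and Power paragraph assumes "With at least 60 subjects completing 2 visits", and section 10 says "We aim to test 60 participants (20 per group, 3 groups) from UCSD".

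The plan does not say what distribution the likelihood ratio statistic is compared with, whether the fits are ML or REML, or whether a small-sample correction applies. It names a panel of 30 cytokines and related markers (section 9, Assessment Outcomes). The only significance level it gives is a two-sided 0.05, and it states that the power calculation does not control type I error over the multiple endpoints.

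**The concern.** The chi-square reference for a likelihood ratio statistic is a large-sample result. ML estimates the residual variance with divisor N and makes no allowance for the estimated group means. In small samples the statistic therefore runs too large and p-values come out too small. An uncorrected likelihood ratio test is normally referred to chi-square, so that is the likely reading of the plan.

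The interaction test is the only analysis listed that compares the change in each outcome across all three arms at once, and the primary aim is a three-arm comparison. The same test is repeated over the microbiome, blood marker and questionnaire outcomes. The results are meant to guide a larger trial, so p-values that are systematically a little too small would bring forward slightly more chance signals than the nominal level implies.

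**Working it through.** **Inputs.** N = 60 completers in 3 arms of 20 (sections 9 and 10); two visits; nominal level 0.05; 30 blood markers (section 9). Assumptions not in the documents: ML fits, a chi-square reference, normal outcomes and, for the exact calculation, complete data at both visits.

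**The plan's own figures.** The plan says: "we will have 80% power (2-sided alpha=0.05) to detect a 0.75 effect-size". The planned enrolment reproduces: 60/(1 − 0.20) = 75. The stated 80% is not reproduced at 20 against 20 (63.7% by the t-test) but roughly is at 30 against 30 (81.5%). That is a separate matter and does not affect this point. The plan gives no figure for the size of the likelihood ratio test beyond the nominal 5%, so there is nothing further to reproduce.

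**Step 1: the statistic.** With two complete visits and a random intercept, the interaction depends only on the change scores. With q = 2 numerator and N − 3 = 57 denominator degrees of freedom,

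T = N × ln(1 + qF/(N − 3)) = 60 × ln(1 + 2F/57),

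where F is the one-way ANOVA statistic on change scores. Under normality and no effect, F follows F(2, 57) exactly.

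**Step 2: true size.** For 2 numerator degrees of freedom, P(F > f) = (1 + 2f/57)^(−57/2), so P(T > t) = exp(−t × 57/120). The chi-square(2) critical value at level α is t = −2 ln α. Substituting gives

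true size = α^(57/60) = α^0.95.

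- At α = 0.05, t = 5.99, and the size is 0.05^0.95 = 0.0581 (1.16 times nominal, an excess of 0.81 percentage points).
- At α = 0.05/30 = 0.00167, the size is 0.00167^0.95 = 0.0023 (1.38 times nominal, an excess of 0.063 percentage points).

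The ratio is α^(−0.05). It rises as α falls, while the absolute excess per test shrinks.

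**Step 3: a 1-df term in the same 60-person model.** Here T = 60 × ln(1 + F/57) with F(1, 57). The chi-square(1) cut-off of 3.84 corresponds to F = 57 × (exp(3.84/60) − 1) = 3.77, and the size is 5.72%.

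**Step 4: check by simulation.** The ML random-intercept test of the interaction was simulated with 160,000 replicates per setting, at within-subject correlations of 0.2, 0.5 and 0.7. Samples were either 60 complete subjects, or 60 complete plus 15 with baseline only (the drop-out the plan allows for). Size was 5.7% to 5.9% at nominal 5%, and 0.21% to 0.25% at nominal 0.167%.

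**Step 5: after correction.** Referring F to F(2, 57) gives exactly 5.0% with complete normal data. The equivalent cut-off for T is −2 × (60/57) × ln 0.05 = 6.31 instead of 5.99. The matching Bartlett-type factor is 60/57 = 1.053; the simulated mean of T divided by its degrees of freedom was 1.052.

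**The case against.** The strongest reply is that this is a small matter in a pilot that openly leaves multiplicity uncontrolled. A move from 5.0% to 5.8% changes no stated decision. Skewed cytokines or zero-heavy taxa may disturb the test more, even after the planned transformations. This is fair, and it sets the priority: the missing multiplicity control is a larger issue.

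A second reply is that the plan does not mention chi-square. That is correct, so the finding is conditional on the default being used. The plan rules out neither that default nor the invalid comparison of REML likelihoods between models with different fixed effects.

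A third is that pairwise comparisons are already covered, since change-score t-tests have exact size under normality. This also stands. A reader might infer that every per-outcome test in the plan rejects too often, and the documents do not support that. The t-tests do not, however, supply the joint three-arm test, and the plan does not say which analysis decides if they disagree.

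A reader might also infer that the error becomes serious at the small thresholds used for cytokines and taxa. The plan uses no such thresholds. The 0.05/30 level is an assumption made here for illustration, the number of taxa is not given, and the excess grows only as a ratio.

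**Conclusion.** The point holds as a minor one. With ML fits, a chi-square reference, normal data and 60 completers, the three-arm group-by-time test has a true type I error of about 5.8% instead of 5% (5.7% for a 1-df term). The simulation shows that the result for the interaction persists with the expected drop-out. The group main effect was not calculated.

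The figure of about 1.4 times nominal applies only if a Bonferroni rule over 30 markers is adopted. The sizes rest on normality and could differ for outcomes that remain skewed after transformation.

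**What to change.** Replace the likelihood ratio sentence with one stating that the mixed models are fitted by REML, and that group, time and group-by-time are tested by F-tests with Kenward-Roger (or Satterthwaite) degrees of freedom. For group-by-time with complete normal data this is exact and equals the ANOVA of change scores. With missing visits it is an approximation.

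If likelihood ratio tests are preferred, state that the models are fitted by ML and that a Bartlett-type correction is applied. For the 2-df interaction with 60 complete subjects, this means dividing the statistic by 60/57.

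The cost is one sentence and slightly larger p-values: a statistic of 5.99 would give p = 0.058 instead of 0.050. No change to sample size or data collection is needed. Neither option addresses multiplicity or non-normal outcomes, which need their own provisions.

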**6. SPECIFIC AIMS**

Primary Aim: In healthy, cognitively intact elderly subjects, determine the effects of an 8-week synbiotic supplement intervention on the stool microbiome (pre- and post-intervention) as compared to *Triphala* alone and placebo.

Secondary Aim: In healthy elderly subjects, examine the effects of an 8-week synbiotic supplementation intervention on inflammatory blood markers compared to herb alone or placebo.

Exploratory Aim 1: In healthy elderly subjects, examine the effects of an 8-week synbiotic intervention on gastrointestinal and psychological health via questionnaires compared to herb alone or placebo.

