
Our overarching research goal is to help reduce early morbidity from aging and mortality associated with infection in the aged by developing probiotics with the potential to enhance the health benefits of *Triphala* to reverse chronic inflammation and stimulate immune robustness. Our project is based on the hypothesis as well as *in vitro* data from our laboratory which demonstrate that the bioactivity of *Triphala* is elicited by the gut microbiome to generate a widened spectrum and abundance of anti-inflammatory compounds. We reason that the *Triphala*-induced benefits to both the elderly as well as persons of all ages can be enhanced by co-administration of specific probiotic species. *Thus, we hypothesize that probiotic formulations consisting of bacterial species capable of mediating the increased digestion, bioabsorption and bioactivity of Triphala will increase and make more uniform the response and impact of Triphala treatment on human populations. We hypothesize that the potent anti-inflammatory Triphala when co-administered with VSL#3 will further reduce inflammation and promote a healthier gut community architecture in the elderly.*

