**11. RECRUITMENT AND PROCEDURES PREPARATORY TO RESEARCH**

**Overview.** A total of 75 participants who are generally healthy and otherwise meet our study criteria will be recruited and randomly assigned to either an 8-week synbiotic group, herb alone, or placebo control with a goal to obtain 60 patients who complete the study (20 in each group) after an estimated 20% attrition. Placebo control subjects will be given the option of having the 8-weeks of herbal synbiotic for directed personal use upon conclusion of the study. [name] has volunteered to help identify individuals who meet criteria for this study. Additional staff members responsible for assisting with recruitment are listed elsewhere in this application.

With this application, we are requesting a Waiver of Documented Consent to conduct the telephone screens. Asking interested individuals whether they meet the basic study criteria over the telephone (age, immune disorder diagnosis, medication use) presents no more than minimal risk of harm and involves no procedures for which written consent is normally required outside of the research context. Written consent will be obtained at the initial, in-person visit before any study questionnaires are administered or research procedures are performed.

With this application, we are also requesting a partial waiver of HIPAA authorization so that our study staff may help clinical staff identify potentially eligible participants using EPIC. When a member of our research team identifies a patient who may be eligible, he or she will then send a secure EPIC email asking the provider if they agree that a given patient is a good candidate for the study and asking the provider to speak with his or her patient about our study. The provider will provide a brief overview of the study during the patient's clinical

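### The 80% power is stated for an unnamed contrast, and at 20 completers per arm it does not hold for synbiotic versus Triphala alone

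*Combined protocol and SAP*

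**What the plan says.** The trial has three arms: synbiotic (Triphala plus VSL#3), Triphala alone, and placebo. Section 6 sets the primary aim as the effect of an "8-week synbiotic supplement intervention on the stool microbiome (pre- and post-intervention) as compared to" Triphala alone and placebo. The secondary aim, on inflammatory blood markers, names the same two comparators.

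Section 9, Statistical Issues, plans two-sample t-tests that "will be used to compare change scores (post-treatment minus pretreatment) in each outcome". The power paragraph assumes a single Cohen's d, an "effect-size (standardized mean difference between groups) of 0.75 based on previous studies", and concludes: "With at least 60 subjects completing 2 visits, we will have 80% power (2-sided alpha=0.05) to detect a 0.75 effect-size". It names no pair of arms and gives no second effect size. It reaches 75 recruits by "allowing for a 20% drop-out/loss-to-follow-up rate and a total of 60 subjects completing the 2 visits".

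The number per arm is stated elsewhere. Section 10 has "We aim to test 60 participants (20 per group, 3 groups) from UCSD", and Section 11 has "60 patients who complete the study (20 in each group) after an estimated 20% attrition".

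Section 7 gives the scientific expectation: "the potent anti-inflammatory Triphala when co-administered with VSL#3 will further reduce inflammation". Triphala is thus expected to work alone, and the probiotic to add to it.

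**The concern.** A power statement for a three-arm trial has to say which comparison it covers and use the number in those arms. This one gives one d, the total number of completers and no contrast, although the aims contain two.

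The comparison with Triphala alone is the one that isolates what VSL#3 adds, which is the hypothesis of Section 7. A reader who takes 80% to apply to it will think the trial well placed to detect an added effect. A non-significant result could then be taken as evidence that the probiotic contributes nothing, and Section 9 says the findings are meant to inform a larger trial.

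**Working it through.** **Inputs.** d = 0.75, two-sided alpha 0.05, 80% power and 60 completers (Section 9, Sample Size and Power); two-sample t-test on change scores (Section 9, Analysis Plan); 20 completers in each of three arms (Sections 10 and 11).

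**Formula.** With n per arm, the noncentrality is λ = d / √(2/n) on 2n − 2 degrees of freedom. Power is the probability that a noncentral t with that λ exceeds the two-sided 5% critical value in absolute size.

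**Step 1: reproduce the plan's figures.**
- Recruitment: 60 / (1 − 0.20) = 75. This agrees.
- Power with 60 as two groups of 30: λ = 0.75 / √(2/30) = 2.90 on 58 df, power 81.5%. This is close to the stated 80%, but it is not the documented design.
- Power with 20 v 20: λ = 0.75 / √(2/20) = 2.37 on 38 df, power 63.7% (66.0% by the normal approximation). The stated 80% is not reproduced.

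**Step 2: try other routes to 80% at d = 0.75.**
- 20 v 20 with the error variance pooled over three arms (57 df): 64.5%.
- 20 v 20, one-sided: 75.3%.
- 25 v 25, that is, all 75 recruits with no loss: 73.8%.
- Overall F test, three arms of 20, largest gap 0.75: 53% with the third mean midway, 66% with two means equal.
- 20 v 40, two arms combined against one: 76.8% (78.2% by the normal approximation, close to 80%, but no such contrast is planned).

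By the t-test, 80% power at d = 0.75 needs 29 per arm. At 20 per arm the d detectable with 80% power is 0.909.

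**Step 3: the two readings of 0.75 at 20 per arm.** Let x be the effect of Triphala over placebo in SD units. The documents give no x. On a common SD, synbiotic v placebo equals x plus synbiotic v Triphala.

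If 0.75 is synbiotic v Triphala, that contrast has 63.7% power. Synbiotic v placebo is then 0.75 + x, with 74.5% power at x = 0.10 and about 80% at x = 0.16.

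If 0.75 is synbiotic v placebo, that contrast has 63.7% power and synbiotic v Triphala is 0.75 − x. With assumed shares for Triphala:

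| Share from Triphala | Synbiotic v Triphala d | Power, 20 per arm | Power, 30 per arm |
|---|---|---|---|
| one quarter | 0.75 × 3/4 = 0.5625 | 41% | 57% |
| one half | 0.75 × 1/2 = 0.375 | 21% | 30% |

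The 30-per-arm column is for comparison only. These shares illustrate direction and scale; they do not come from the protocol. A share near zero gives nearly the full 63.7% (62.6% at x = 0.01).

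**Step 4: precision.** At 20 per arm the 95% confidence interval for a difference in mean change has half-width t(0.975, 38) × √(2/20) = 2.024 × 0.316 = 0.64 SD.

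**The case against.** A reader might infer more: that 0.75 is applied to both comparisons, that Section 7 makes them unequal, and that 80% therefore cannot hold for synbiotic v Triphala alone however 60 people are divided. The documents do not support this, for four reasons.

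- The power paragraph assigns 0.75 to no contrast. If it belongs to synbiotic v Triphala, Section 7 is satisfied by a larger difference from placebo.
- Power to detect a given d is conditional on that d. Two contrasts can be powered for the same detectable difference while their true effects differ, so unequal effects do not by themselves falsify the statement.
- With two groups of 30, power is 81.5% if 0.75 is the synbiotic v Triphala effect. Even if 0.75 is the placebo contrast, it is 80.5% when Triphala's own effect is 0.01 SD.
- Standardised differences add only on a common SD, and Section 7 also expects the probiotic to make responses less variable. The ordering is explicit for inflammation, and less so for the microbiome, which is the primary aim.

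It can also be said that the study is presented as an exploratory pilot, that it admits no type I error control for its many endpoints, and that nowhere does it say a null result would be read as no added effect.

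All of this stands against the wider inference. It does not rescue the figure. The documented design has 20 per arm, where power at the full 0.75 is 63.7% whichever pair is meant. Pilot status bears on how much a low figure matters, not on whether it is correct.

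**Conclusion.** The concern holds in a limited form. The contrast for d = 0.75 is unnamed, and at the documented 20 completers per arm the stated 80% is about 64% at that d. For synbiotic v Triphala alone, 64% is the best case among effects up to 0.75. The shortfall comes from the arm size. Unequal effects deepen it only if 0.75 refers to placebo and Triphala is active; the 41% and 21% then depend on assumed shares and a common SD.

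The calculation takes 0.75 to be on the SD of the change scores, as the planned test requires. If it were on the SD of single measurements, the change-score effect would be 0.75 / √(2(1 − ρ)), and 20 per arm would reach 80% at a pre-post correlation ρ of about 0.66. The documents state no correlation and no such scaling, so this remains an assumption that the authors would have to declare.

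The correction should be made because the plan relies on this figure, and the contrast most exposed is the one that carries the added-benefit hypothesis.

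**What to change.** In Section 9, Sample Size and Power:

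1. Name the pair of arms to which d = 0.75 refers, and state that it is on the change-score SD.
2. Replace 80% with about 64% at d = 0.75 and 20 completers per arm, and add that 80% would need d of about 0.91.
3. For synbiotic v Triphala alone, give a separate assumed d with its power at 20 per arm. Otherwise, state that this contrast is not powered and will be reported as an estimate with a 95% confidence interval, expected half-width about 0.64 SD.
4. Add that a non-significant difference between synbiotic and Triphala alone will not be interpreted as no added effect of VSL#3.

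The cost is protocol wording and a less favourable stated figure. Recruitment stays at 75 and no extra participants are needed.

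### The stated 80% power for d = 0.75 does not hold with 20 completers per arm: a two-sample t-test between two arms has about 64%

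*Combined protocol and SAP*

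**What the plan says.** The Sample Size and Power paragraph (Section 9, Statistical Issues) assumes a Cohen's d "effect-size (standardized mean difference between groups) of 0.75 based on previous studies" and concludes: "With at least 60 subjects completing 2 visits, we will have 80% power (2-sided alpha=0.05) to detect a 0.75 effect-size". It then raises recruitment to 75 for 20% drop-out. It adds that Type I error was not controlled for multiple endpoints and that the study is a small pilot.

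The power paragraph does not give a number per arm. Other sections do:

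- Section 10: "We aim to test 60 participants (20 per group, 3 groups) from UCSD".
- Section 11, Overview: "60 patients who complete the study (20 in each group) after an estimated 20% attrition".

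The Analysis Plan (Section 9) says that two-sample t-tests will be "used to compare change scores (post-treatment minus pretreatment) in each outcome". It also lists O'Brien's test for each hypothesis and mixed models with a group-by-time interaction. The primary aim (Section 6) compares the synbiotic with *Triphala* alone and with placebo. The secondary aim does the same: "intervention on inflammatory blood markers compared to herb alone or placebo".

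**The concern.** A two-sample t-test between arms in this design uses two of the three groups, so 40 of the 60 completers. The power sentence gives only the total of 60, and its 80% fits a trial in which all 60 sit in two groups. No passage pools two arms for analysis.

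This sentence is the only numerical justification for the sample size. The results are also meant to inform a larger trial. A reader who trusts 80% would give a null comparison too much weight, for example by concluding that the probiotic adds nothing to the herb, when the real chance of missing the planned effect is nearly twice the 20% implied.

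**Working it through.** **Inputs from the documents**

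- Two-sided alpha 0.05, power 80%, d = 0.75, 60 completers (Section 9, Sample Size and Power)
- Three arms of 20 completers (Sections 10 and 11)
- Two-sample t-test on change scores (Section 9, Analysis Plan)
- No pre-post correlation, no between-outcome correlation and no pooling of arms are given

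**Formula.** The power of a two-sample t-test comes from the noncentral t distribution with df = n1 + n2 − 2 and noncentrality δ = d·√(n1·n2/(n1 + n2)). It is the probability that |t| exceeds the two-sided 5% critical value.

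**Step 1: look for the stated 80%.** With all 60 in two arms, δ = 0.75·√(900/60) = 0.75·√15 = 2.905 on 58 df, and power is 81.5%. The smallest equal arms that reach 80% are 29 v 29 (80.1%); 28 v 28 gives 78.7%. So 80% is consistent with a two-group calculation.

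**Step 2: the design as described.** With 20 v 20, δ = 0.75·√(400/40) = 0.75·√10 = 2.372 on 38 df (critical value 2.024), and power is **63.7%**.

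**Step 3: other configurations, d = 0.75, two-sided 0.05**

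| Comparison | Power |
|---|---|
| 20 v 20, own two arms (38 df) | 63.7% |
| 20 v 20, normal approximation | 66.0% |
| 20 v 20, error pooled over three arms (57 df) | 64.5% |
| 25 v 25 (all 75 retained) | 73.8% |
| 40 v 20 (two arms pooled; not planned) | 76.8% |
| Three-group F-test, means 0, 0.375, 0.75 | 53.2% |
| Three-group F-test, one arm differs by 0.75 | 66.3% |

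None reaches 80%. A one-sided t-test at 20 v 20 would give 75.3%, and the plan says two-sided.

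**Step 4: detectable effect.** Solving for d at 80% power with 20 v 20 gives d = 0.91 (0.90 with 57 error df), against the 0.75 stated.

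**Step 5: sensitivity to the scale of d.** Steps 2 to 4 take 0.75 in SDs of the change score. If it is in raw-score SDs, with equal SDs at both visits, the change score has SD·√(2(1 − r)), where r is the pre-post correlation. The effect on the change score is then 0.75/√(2(1 − r)). The documents give no r, so these values are assumptions:

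| r (assumed) | 0.3 | 0.5 | 0.6 | 0.66 | 0.7 |
|---|---|---|---|---|---|
| Effect in change-score SDs | 0.634 | 0.750 | 0.839 | 0.910 | 0.968 |
| Power, 20 v 20 | 49.8% | 63.7% | 73.4% | 80.0% | 84.7% |

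With baseline adjustment instead (effect 0.75/√(1 − r²), 37 df), power is 76.0% at r = 0.5 and 82.3% at r = 0.6, and it reaches 80% at r = 0.566.

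**Step 6: sensitivity to O'Brien's test.** Suppose d = 0.75 on every one of m outcomes, with common between-outcome correlation ρ. The equally weighted composite then has effect 0.75·√(m/(1 + (m − 1)ρ)). For m = 3, power at 20 v 20 is 88.6% (ρ = 0.3), 80.8% (ρ = 0.5) and 73.4% (ρ = 0.7). Reaching 80% needs ρ of at most about 0.36 (m = 2), 0.52 (m = 3) or 0.60 (m = 5).

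**Step 7: drop-out.** 60/(1 − 0.20) = 75. This step is correct.

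**The case against.** The power paragraph does not name the test, the contrast, the SD scale or the success criterion behind its 80%. The Analysis Plan says two-sample and never says pairwise. It lists three analyses without naming one as primary. Several readings reach about 80% with 20 per arm:

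- d in raw-score SDs with a pre-post correlation of 0.66 or more.
- O'Brien's test with the full effect on every outcome. For a long list of outcomes, such as the 30-analyte panel, the tolerable between-outcome correlation rises to about 0.67.
- At least one of the two synbiotic comparisons significant. With true means 0.75, 0 and 0 and no multiplicity adjustment, simulation gives 79.3%.

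The study is also a self-described pilot with feasibility outcomes.

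Part of this stands. The pairwise reading is inferred, although three separate arms and the wording of the aims leave no other natural use of a two-sample test. The 64% depends on the scale of d. The origin of the 80% is not known, so it should not be asserted that a two-arm formula was used.

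The rest does not rescue the sentence. Each route to 80% needs a correlation, an effect on every outcome or a success criterion that the documents do not state, and a lower pre-post correlation makes power worse. Pilot status is a good reason not to enlarge the trial, but it does not make the number right. The caveat on multiple endpoints does not address the three-arm split. Adjusting for two or three pairwise comparisons (Bonferroni) would lower power further, to about 52% or 46%.

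**Conclusion.** The concern holds. For the planned change-score t-test between two arms of 20, power at d = 0.75 is 63.7% (64.5% with pooled three-arm error), about 16 percentage points below the stated 80%. The probability of missing the planned effect in each comparison is about 36%. This rests on three conditions: comparisons between two arms of 20 completers, d in change-score SD units (or raw-score SDs with a pre-post correlation of 0.5), and no multiplicity adjustment. The error lies in the stated justification. It does not bias the comparisons themselves.

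**What to change.** Replace the power sentence with wording such as:

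> With 20 completers per arm, each pairwise two-sample comparison of change scores has about 64% power (two-sided alpha 0.05, unadjusted for multiple comparisons) for d = 0.75 in change-score SD units, and 80% power for d = 0.91.

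If the team intended another basis, such as raw-score SDs, baseline adjustment or O'Brien's test, state that separately with the assumed correlation and its source.

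The cost is one sentence of protocol text and a less favourable figure. No extra participants are needed for this correction, and the 75 recruited, the allocation, the tests and the endpoints do not change. For reference, keeping 80% at d = 0.75 for each comparison would take 29 completers per arm: 3 × 29 = 87 completers and, at 20% drop-out, 87/0.8 = 108.75, so 109 recruited. A pilot need not do this, provided the stated power is correct.
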